6.2.1. Rationale for Exclusion of Certain Study Candidates

Patients who were not suitable candidates to receive mirikizumab treatments at the end of the originator study treatment period will be excluded from this study, which is intended to evaluate the safety and efficacy of long-term mirikizumab treatment.

6.3. Lifestyle Restrictions

Study participants should be instructed not to donate blood or blood products during the study or for 12 weeks following their last dose of investigational product.

6.4. Screen Failures

Screen failures are not applicable as study participation is dependent on completion of the originator studies and not the screening process.

7. Treatments

7.1. Treatments Administered

This study involves an evaluation of long-term maintenance of response to mirikizumab 250 mg or 125 mg administered SC for up to 208 weeks of dosing. [Table AMAH.3](#) shows the treatment regimens.

Table AMAH.3. Treatment Regimens

Originator Study	Treatment at End of Originating Study	Treatment in Study AMAH (Q8W)
AMBK	250 mg miri Q4W	250 mg miri (2 x 1-mL miri PFS)
AMAF	300 mg miri, Q8W fixed or PRN	250 mg miri (2 x 1-mL miri PFS)
	30 mg or 100 mg miri PRN	125 mg miri ^a (1 x 1-mL miri PFS plus 1 x 1-mL placebo PFS ^b)
AMAJ	250 mg miri Q8W or secukinumab	250 mg miri (2 x 1-mL miri PFS)
	125 mg miri Q8W	125 mg miri ^a (1 x 1-mL miri PFS plus 1 x 1-mL placebo PFS ^b)
AMAK	250 mg miri Q8W or placebo	250 mg miri (2 x 1-mL miri PFS)
	125 mg miri Q8W	125 mg miri ^a (1 x 1-mL miri PFS plus 1 x 1-mL placebo PFS ^b)

Abbreviations: miri = mirikizumab; PFS = prefilled syringe; PRN = as needed; Q4W = every 4 weeks; Q8W = every 8 weeks.

^a Patients receiving 125 mg Q8W may be eligible to escalate to 250 mg Q8W (see Section 7.4)

^b Placebo will be administered only until study treatments are unblinded (see Section 7.3 describing how long treatments are blinded).

Administration:

Detailed instructions for investigational product administration will be provided by the Sponsor, and the investigational product will be administered at the site by clinical staff until Visit 14, at which time site staff will train patients on self-injection and will provide them with a log to track their doses at home.

Following Visit 14, injections will be self-administered SC by the patient or caregiver. It is recommended that these injections be administered away from the investigational site. If the patient or caregiver is not able to administer any dose throughout the study, study site staff may administer that injection.

Refer to the appropriate *Manual Syringe Directions for Use* provided by the sponsor for the investigational product. Note that in the case a study drug injection is performed in an arm, it is not to be given in the same arm from which patient blood samples, including PK samples, are drawn at relevant visits.

Study Drug Administration Logs will be dispensed to each patient for recording pertinent data about each injection; details of the use of these logs are provided in Section 7.2.1. Possible injection sites are identified in the *Manual Syringe Directions for Use*. The injection site may be rotated to another area for subsequent doses.

The investigator or his/her designee is responsible for the following:

- Explaining the correct use of the investigational agent(s) to the site personnel,
- Verifying that instructions are followed properly,
- Maintaining accurate records of investigational product dispensing and collection,
- At the end of the study returning all unused medication to Eli Lilly and Company (Lilly), or its designee, unless the Sponsor and sites have agreed all unused medication is to be destroyed by the site, as allowed by local law

At the time of unblinding, patients, site personnel and the Sponsor will become unblinded so that patients on the 125 mg miri can stop receiving a 1 x 1-mL placebo PFS (see [Table AMAH.3](#)).

7.1.1. Packaging and Labeling

Mirikizumab and placebo will be supplied to the investigator by Lilly. Clinical trial materials will be labeled according to the country's regulatory requirements. All investigational products will be stored, inventoried, reconciled, and returned or destroyed according to applicable regulations. Clinical trial materials are manufactured in accordance with current Good Manufacturing Practices (GMP).

Investigational product will be supplied as single-use solution in prefilled syringes containing mirikizumab or placebo. The 1-mL syringe of mirikizumab is manufactured to contain 125 mg of the drug.

Mirikizumab cannot be distinguished visually from placebo.

Investigational product will be provided with study-specific labels. Syringes will be supplied in cartons, with the appropriate quantity specific to the planned dispensing schedule of the investigational product.

7.2. Method of Treatment Assignment

Patients who meet all criteria for enrollment will be assigned to double-blind treatment at Visit 1 based on the ending treatment regimen of the originating study (see [Table AMAH.3](#)). The interactive web-response system (IWRS) will be used to assign prefilled syringes containing investigational product to each patient. Investigational product will be dispensed according to the Schedule of Activities (Section 2). Site personnel will confirm that they have located the correct prefilled syringes by entering a confirmation number found on the prefilled syringes into the IWRS.

7.2.1. Selection and Timing of Doses

Study visits at which the investigational product is administered are preferred, if possible, to occur on the same day of the week. In any case, the study visits should occur within the visit window specified on the Schedule of Activities (see Section 2). The actual time of all dose administrations will be recorded in the patient's electronic case report form (eCRF). Study drug will be administered by site personal at Visits 1-13. Starting with Visit 14 patients should self-administer study drug on the day of the visit, and then every 8 weeks thereafter, preferably on the same day of the week.

7.3. Blinding

This is a double-blind study until the originating studies AMAJ and AMAK have had database lock and dosing for those studies is no longer blinded. The blinding applies to patients, site personnel, and Sponsor personnel.

Personnel in the originator Studies AMAF and AMAJ performing unblinded tasks (e.g., study drug dosing/dispensing) will by default know the treatment assignments of individual patients in Study AMAH by the protocol design. If these unblinded site personnel in the originator Studies AMAF and AMAJ also have a role in Study AMAH, they must assume the same responsibilities taken in the originator study for these patients and **must not** be involved in any patient assessment activities, seek any information related to these patients beyond their allowed activities, discuss the treatment assignment with the patient or with the blinded personnel. Principal Investigators will need to ensure that the blinded conditions of the originating studies are maintained during Study AMAH until database lock has occurred and dosing for those studies is no longer blinded.

Emergency unblinding for AEs may be performed through the IWRS, which may supplement or take the place of emergency codes generated by a computer drug-labeling system. This option may be used **ONLY** if the patient's well-being requires knowledge of the patient's treatment assignment. All actions resulting in an unblinding event are recorded and reported by the IWRS.

If an investigator, site personnel performing assessments, or patient is unblinded before the study dosing is no longer blinded, the patient may continue the study, unless there are safety or benefit/risk reasons for the patient not to continue the study as determined by the principal investigator or Sponsor.

In case of an emergency, the investigator has the sole responsibility for determining if unblinding of a patient's treatment assignment is warranted for medical management of the event. The patient's safety must always be the first consideration in making such a determination. If a patient's treatment assignment is unblinded, Lilly must be notified immediately. If the investigator decides that unblinding is warranted, it is the responsibility of the investigator to promptly document the decision and rationale and notify Lilly as soon as possible.

7.4. Dosage Modification

After Study AMAH dosing is no longer blinded, patients who in the opinion of the investigator have experienced significant clinically meaningful loss of efficacy during study participation may be increased from 125 mg mirikizumab Q8W to 250 mg mirikizumab Q8W if it is determined by the patient and the investigator that the patient might benefit from additional study drug in order to maintain satisfactory disease control. All patients who increase dosing to 250 mg mirikizumab Q8W will remain on this dose until completion of the study or early discontinuation. No other dose adjustments are permitted in Study AMAH.

7.5. Preparation/Handling/Storage/Accountability

The investigator or his/her designee is responsible for the following:

- Confirming that appropriate temperature conditions have been maintained during transit for all study treatment received, and any discrepancies are reported and resolved before use of the study treatment.
- Ensuring that only participants enrolled in the study may receive study treatment and only authorized site staff may supply or administer study treatment. All study treatments must be stored in a secure, environmentally controlled, and monitored (manual or automated) area in accordance with the labeled storage conditions, with access limited to the investigator and authorized site staff.
- The investigator, institution, or the head of the medical institution (where applicable) is responsible for study-treatment accountability, reconciliation, and record maintenance (such as, receipt, reconciliation, and final disposition of records).

Detailed instructions regarding supplies and preparation and handling of investigational products will be provided by the Sponsor.

Investigational products will be supplied by Lilly or its representative, in accordance with current GMP and will be supplied with lot numbers, expiry dates, and certificates of analysis, as applicable. All investigational products will be stored, inventoried, reconciled, and destroyed according to applicable regulations.

Mirikizumab, placebo, and secukinumab should be transported and stored in refrigerated conditions at 2°C to 8°C (36°F to 46°F).

7.6. Treatment Compliance

Deviations from the prescribed dosage regimen should be recorded in the eCRF.

Every attempt will be made to select patients who have the ability to understand and comply with the study instructions. The investigator is responsible for discussing methods to ensure high treatment compliance with the patient.

If a patient is noncompliant with study procedures and/or investigational product administration, the investigator should assess the patient to determine the reason for noncompliance and educate and/or manage the patient as appropriate to improve compliance. If, in consultation with Lilly or its designee, the noncompliance is deemed to be significant, or if further noncompliance occurs, the patient may be discontinued from the study.

7.7. Concomitant Therapy

All concomitant medications taken during the study must be recorded on the Concomitant Medication eCRF. All patients should maintain their usual medication regimens for concomitant conditions or diseases throughout the study, unless those medications are specifically excluded in the protocol.

Patients taking concomitant medications should be on stable dosages at the time of baseline and should remain at stable dosages throughout the study, unless changes need to be made because of AEs. Additional systemic drugs are to be avoided during the study, unless required to treat AEs. If the need for concomitant medication arises for an AE or for appropriate medical management (including the limited use of therapeutic agents which, if used under treatment regimens other than for treating an AE or for appropriate medical management, might be considered psoriasis therapies), the investigator should base decisions on the patient and clinical factors. Other medications may be allowed if they are approved by the Sponsor or its designee.

Use of nonlive (killed, inactivated, or subunit) vaccinations are allowed for all patients; however, their efficacy with concomitant mirikizumab is unknown. Use of live, attenuated vaccines is prohibited.

Classes of therapies not permitted during the course of the study or permitted with use restrictions are specified in [Table AMAH.4](#) below (also see the section Exclusion Criteria [Section 6.2]).

Table AMAH.4. Excluded Classes of Concomitant Medications or Classes with Restricted Use

Drug Class	Allowed for Chronic Use	Allowed with Restrictions	Conditions for Allowed Use
Topical treatment for psoriasis or any other skin condition (including, but not limited to, corticosteroids, crisaborole, anthralin, calcipotriene, topical Vitamin D derivatives, retinoids, tazarotene, pimecrolimus, tacrolimus, emollients, and other nonprescription topical products containing urea, >3% salicylic acid, alpha- or beta-hydroxyl acids)	N	N	
Topical treatment for psoriasis limited to face, axilla, or genitalia	N	Y	Mild or least potent topical steroids will be permitted for use limited to the face, axilla, and/or genitalia, as needed. These topical medications should not be used within approximately 24 hours prior to study visits.
Photochemotherapy (for example, PUVA)	N	N	
Phototherapy (for example, UVA, UVB, excimer laser)	N	N	
Biological immunomodulating agents (for example, alefacept, briakinumab, efalizumab, ixekizumab, secukinumab, etanercept, adalimumab, infliximab, certolizumab)	N	N	
Other systemic immunomodulating treatments (for example, MTX, cyclosporine A, corticosteroids, cyclophosphamide)	N	N	

Drug Class	Allowed for Chronic Use	Allowed with Restrictions	Conditions for Allowed Use
Systemic immunomodulating treatments (corticosteroids only)	N	Y	Limited use of systemic corticosteroids ONLY as needed for limited, short-term medical management of TEAE may be considered. Such drug class might be considered psoriasis therapy if used under other regimens. Limited use during TEAE management is considered to not be consistent with psoriasis therapy.
Systemic psoriasis therapies (for example, retinoids, fumarates, apremilast)	N	N	
Bacillus Calmette-Guerin (BCG) vaccinations or live virus vaccinations (BCG prohibited for 12 months before baseline, live vaccinations prohibited for 12 weeks before baseline. Both are prohibited throughout the study and for 12 weeks after discontinuation of study drug).	N	N	
Any investigational treatment	N	N	

Abbreviations: MTX = methotrexate; N = No; PUVA = psoralen and ultraviolet A; TEAE = treatment-emergent adverse event; UVA = ultraviolet A; UVB = ultraviolet B; Y = Yes.

Topical therapies allowed during the study include shampoos that do not contain >3% salicylic acid, corticosteroids, coal tar, or vitamin D3 analogues; topical moisturizers/emollients and other non-prescription topical products that do not contain urea, >3% salicylic acid, alpha- or beta-hydroxyl acids, corticosteroids, or vitamin D3 analogues; and bath oils and oatmeal bath preparations. These topical therapies are not to be used within 12 hours prior to a study visit.

For patients who have entered the Post-Treatment Follow-Up Period, psoriasis therapy with another agent(s), as determined appropriate by the investigator, is allowed.

7.8. Treatment after the End of the Study

7.8.1. Treatment after Study Completion

Mirikizumab will not be made available to patients who either discontinue early from Study AMAH or complete Study AMAH.

7.8.2. *Special Treatment Considerations*

7.8.2.1. Management of Hypersensitivity Events, Including Injection Site Events

All biological agents carry the risk of systemic allergic/hypersensitivity events. Clinical manifestations of these events may include, but are not limited to, the following:

- Skin rash
- Pruritus (itching)
- Urticaria (hives)
- Angioedema (for example, swelling of the lips and/or tongue)
- Anaphylactic events

Sometimes, these events can be life-threatening. Proteins may also cause redness, itching, swelling, or pain locally at the injection site. Therefore, all patients should be closely monitored for signs or symptoms that could result from such events, educated on the signs or symptoms of these types of events, and instructed to contact the study site immediately if any of the symptoms are experienced following an injection. If a patient experiences an acute hypersensitivity event after an injection of the investigational product, he or she should be managed appropriately and given instructions to receive relevant supportive care.

Additionally, for an event judged by the investigator to be a potential systemic hypersensitivity event, blood samples will be collected for PK, immunogenicity, and exploratory hypersensitivity analyses at, or as close as possible to

1. the onset of the event,
2. the resolution of the event, and
3. 30 (\pm 3) days following the event.

Exploratory hypersensitivity samples may, as appropriate for the clinical presentation,

- be analyzed for tryptase (a marker of basophil/mast cell activation),
- have a complement panel performed (assess immune complex formation), and
- have a cytokine panel performed.

See also Section [9.4.4](#).

Patients who develop clinically significant systemic hypersensitivity events following administration of investigational product should be discontinued from the study and not receive further doses of investigational product, with or without premedication (see Section [8.2](#)).

8. Discontinuation Criteria

8.1. Discontinuation from Study Treatment

8.1.1. *Permanent Discontinuation from Study Treatment*

Patients for whom investigational product should be permanently discontinued, irrespective of the reason, should complete the Post-Treatment Follow-Up and then be permanently discontinued from the study. Section 8.2 provides the list of criteria for permanent discontinuation of patients from study treatment and the study.

Patients discontinuing from the investigational product prematurely for any reason should complete AE and other follow-up procedures per Section 2 (Schedule of Activities), Section 5.1.3 (Post-Treatment Follow-up Period), Section 9.2 (Adverse Events), and Section 9.4 (Safety) of this protocol.

8.1.2. *Temporary Interruption (Withholding) of Study Treatment*

Some possible reasons for temporarily withholding investigational product include, but are not limited to, the following:

- Development of:
 - Serious or opportunistic infections, as described in Section 9.2.3).
 - Hypertension (see Section 9.4.2.1).
 - Latent tuberculosis (TB) infection (LTBI) (see Section 9.4.5.2).
 - Positive hepatitis B virus (HBV) deoxyribonucleic acid (DNA) results that are below the level of quantification (see Section 9.4.5.3).
 - Hepatic event or liver test abnormality: Investigational product should be withheld and additional testing performed following consultation with the Lilly-designated medical monitor, if the results of repeat tests following elevated alanine aminotransferase (ALT), alkaline phosphatase (ALP) or total bilirubin level (TBL) include one of the following (Section 9.4.6.1):
 - $ALT \geq 3 \times$ upper limit of normal (ULN) and $TBL < 2 \times ULN$
 - $ALP \geq 2 \times ULN$ and $TBL < 2 \times ULN$
 - $TBL \geq 2 \times ULN$ without increase from baseline in ALT/aspartate aminotransferase (AST)/ALP.
- Surgery: Patients requiring surgery at any time during the study should interrupt administration of the investigational product, beginning 8 weeks before the surgery or as early as possible within 8 weeks of surgery, and resume administration of the investigational product only after complete wound healing.

Cases that may merit temporary withholding of the study treatment should be discussed with the medical monitor. The medical monitor, in consultation with the investigator, will determine when it is appropriate to recommence study treatment.

8.1.3. Discontinuation of Inadvertently Enrolled Patients

If the Sponsor or investigator identifies a patient who did not meet enrollment criteria and was inadvertently enrolled, then the patient should be discontinued from study treatment, unless there are extenuating circumstances that make it medically necessary for the patient to continue on the study treatment. If the investigator and the Sponsor-designated medical monitor agree that it is medically appropriate to continue, the investigator must obtain documented approval from the Sponsor-designated medical monitor to allow the inadvertently-enrolled patient to continue in the study with or without treatment with the investigational product. Safety follow up is as outlined in Section 2 (Schedule of Activities), Section 9.2 (Adverse Events), and Section 9.4 (Safety) of this protocol.

8.2. Discontinuation from the Study

Patients should permanently discontinue the investigational product, complete the Post-Treatment Follow-up, and then permanently discontinue from the study for any of the following reasons:

- **Patient Decision**
 - The patient requests to be either discontinued from investigational product or withdrawn from the study.
- **Discontinuation due to a hepatic event or liver test abnormality.** Patients who are discontinued from investigational product due to a hepatic event or liver test abnormality should have additional hepatic safety data collected via eCRF.

Discontinuation of the investigational product for abnormal liver tests **should be** considered by the investigator when a patient meets one of the following conditions after consultation with the Lilly-designated medical monitor:

- ALT or AST >8xULN
- ALT or AST >5xULN for more than 2 weeks
- ALT or AST >3xULN and TBL >2xULN or international normalized ratio (INR) >1.5
- ALT or AST >3xULN, with the appearance of fatigue, nausea, vomiting, right upper-quadrant pain or tenderness, fever, rash, and/or eosinophilia (>5%)
- ALP >3xULN
- ALP >2.5xULN and TBL >2xULN

- ALP >2.5xULN, with the appearance of fatigue, nausea, vomiting, right quadrant pain or tenderness, fever, rash, and/or eosinophilia (>5%)
- In addition, patients who meet any one of the following criteria should be discontinued from the investigational product, enter the Post-Treatment Follow-Up Period, and discontinue from the study:
 - Total white blood cell count <2000 cells/ μ L (<2.00x10³/ μ L or <2.00 GI/L).
 - Lymphocyte count <500 cells/ μ L (<0.50x10³/ μ L or <0.50 GI/L).
 - Platelet count <50,000 cells/ μ L (<50x10³/ μ L or <50 GI/L).
 - Changes in blood pressure (BP) (systolic BP at \geq 160 mm Hg plus \geq 20 mm Hg increase from baseline [Week 0; Visit 2]; and/or diastolic BP at \geq 100 mm Hg plus \geq 10 mm Hg increase from baseline) that do not respond following maximal allowed intervention (further explanation in Section 9.4.2 of this protocol).
 - The patient experiences a severe AE, an SAE, or a clinically significant change in a laboratory value that, in the opinion of the investigator, merits the discontinuation of the investigational product.
 - Clinically significant systemic hypersensitivity event following administration of investigational product.
 - The patient becomes pregnant.
 - The patient develops a malignancy (note: patients may be allowed to continue if they develop no more than 2 non-melanoma skin cancers during a 12-month period).
 - Any patient who has a change in disease phenotype at any time (for example, a change to pustular psoriasis).
 - It is recommended that the patient be assessed by an appropriately trained professional to assist in deciding whether the patient is to be discontinued from study treatment if:
 1. The patient, at any time during the study, scores a 3 for Item 12 (Thoughts of Death or Suicide) on the 16-item Quick Inventory of Depressive Symptomatology (QIDS-SR16);OR
 2. The patient develops active suicidal ideation with some intent to act with or without a specific plan (“yes” to Question 4 or 5 on the “Suicidal Ideation” portion of the Columbia-Suicide Severity Rating Scale [C-SSRS])OR

3. The patient develops suicide-related behaviors as recorded on the C-SSRS.
 - The patient develops active TB or HIV/AIDS during the study.
 - The patient becomes HBV DNA positive or hepatitis C virus (HCV) ribonucleic acid (RNA) positive. The patient should be referred to a specialist physician (see Sections 8.1.2 and 9.4.5.3 for HBV, and Section 9.4.5.4 for HCV).
- Patients will also be permanently discontinued from study drug, complete the Post-Treatment Follow-up, and then permanently discontinue from the study in the following circumstances:
 - Enrollment in any other clinical study involving an investigational product or enrollment in any other type of medical research judged not to be scientifically or medically compatible with this study
 - Participation in the study needs to be stopped for medical, safety, regulatory, or other reasons consistent with applicable laws, regulations, and Good Clinical Practice (GCP)
 - Investigator decision
 - The investigator decides that the patient should be discontinued from the study
 - If the patient, for any reason, requires treatment with another therapeutic agent that has been demonstrated to be effective for treatment of the study indication, discontinuation from the study occurs prior to introduction of the new agent

Patients permanently discontinuing from the investigational product, completing the Post-Treatment Follow-Up, and permanently discontinuing from the study prematurely for any reason should complete AE and other safety follow-up per Section 2 (Schedule of Activities), Section 5.1.3 (Post-Treatment Follow-up Period), Section 9.2 (Adverse Events), and Section 9.4 (Safety) of this protocol.

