- j These assessments should be completed before administration of IP; before the patient's clinical examination; before the patient receives any tests or results; and before the patient's health, health data, or emotions are discussed.
- k Unscheduled blood chemistry and hematology panels may be performed at the discretion of the investigator. See [Appendix 2](#), for details.

- ^l Any enrolled patient who is HBcAb+ in the originator trial will undergo monitoring of HBV DNA with HBV DNA testing (see Section 9.4.5.3). Any patient with a positive HBV DNA test at any time must be discontinued from the study and receive appropriate follow-up medical care, including consideration for antiviral therapy.
- ^m Any enrolled patient with a history of HCV infection (tested positive for HCV antibody in the originator study) who develops elevated ALT >3xULN will be tested for HCV RNA (see Section 9.4.5.4). Any patient with a positive HCV RNA test must be discontinued from the study and receive appropriate follow-up medical care, including consideration for antiviral therapy.
- ⁿ Immunogenicity samples should be collected prior to dosing on visits when mirikizumab is administered. A sample will be obtained at unscheduled visits if a patient develops an acute hypersensitivity event after administration of IP (see Section 7.8.2.1).
- ^o Sample from last visit of originator study should be used. If no sample <4 weeks old is available, then a baseline sample should be collected in this study.
- ^p Scheduled pharmacokinetic samples are taken as an aliquot from the immunogenicity sample. Unscheduled pharmacokinetic samples, obtained if a patient develops an acute hypersensitivity event after administration of IP (see Section 7.8.2.1), will be collected in a separate tube. To be performed only on women of child-bearing potential. Between visits, urine pregnancy tests are to be performed monthly at home.
- ^r If a patient discontinues IP early, the patient will complete the ETV and then enter the Post-Treatment Follow-up Period (Visit 801 and Visit 802).
- ^s Urinalysis assessed only for early termination due to an adverse event for which urinalysis is clinically indicated.

3. Introduction

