5.1.3. Post-Treatment Follow-Up Period (12 Weeks)

All patients, whether they discontinue early for any reason or complete study treatment, will enter the 12-week Post-Treatment Follow-Up Period (Visit 801 and Visit 802) of Study AMAH.

For patients who have entered the Post-Treatment Follow-Up Period, psoriasis therapy with another agent(s), as determined appropriate by the investigator, is allowed.

[Figure AMAH.1](#) illustrates the study design.

Abbreviations: LV = last study visit; miri = mirikizumab given as subcutaneous injection (SC); PRN=as needed; pts = patients; Q8W =every 8 weeks; V = visit; W or w = week.

^aPatients will remain blinded to treatment until the last patient completes the last originator study.

^bPatients receiving 125 mg Q8W may be eligible to escalate to 250 mg Q8W; see Section 7.4

Figure AMAH.1. Illustration of study design for Clinical Protocol I6T-MC-AMAH.

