Amendment Summary for Protocol I6T-MC-AMAH Amendment (a)

Section # and Name	Description of Change	Brief Rationale
Global	Various typos fixed and clarifications made	
Section 2. Schedule of Activities	
 Added “temperature” to Vital Signs Added immunogenicity and associated PK sample to V1, for patients with no sample within prior 4 weeks 	
 Regulatory request from US FDA Ensures continuity of immunogenicity sampling
Section 5.1.3. Post-Treatment Follow-Up Period (12 Weeks)	Added ability for patients to receive psoriasis therapy with another agent(s)	Allow patients not receiving benefit from study drug to access other treatments more quickly
Section 6.1. Inclusion Criteria	Added that local contraception guidelines must be followed	Allow sites to meet local regulatory requirements
Section 7.3. Blinding	Added text to clarify the roles and responsibilities of site personnel who know the treatment assignments of patients in Study AMAH, through their work in an originating study	Original protocol assumed all personnel start the study blinded, which is not necessarily true as patients continue from an originator study into this one with the same site personnel.
Section 7.8.2.1. Management of Hypersensitivity Events, Including Injection Site Events	
 Added that if a patient experiences an acute hypersensitivity event after an injection of the investigational product, blood samples will be collected for PK, immunogenicity, and exploratory hypersensitivity analyses “Patients who develop clinically significant systemic hypersensitivity events following administration of investigational product, who do not respond to symptomatic medication, or whose event results in clinical sequelae (for example, hospitalization), should be discontinued from the study” 	
 To align this section with rest of the protocol. Alignment with commitment to US FDA

Section 8.2 Discontinuation from the Study (sixth subbullet of third bullet point)	“Clinically significant systemic hypersensitivity event following administration of investigational product that does not respond to symptomatic medication or results in clinical sequelae. ”	Alignment with commitment to US FDA

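### Protocol 8.2 holds back another effective psoriasis agent until the patient has left the study, whereas Protocol 5.1.3, 7.7 and SAP 5.1 allow it on entry into follow-up (minor wording conflict)

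*Protocol*

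**What the plan says.** **The restriction.** The final bullet of Protocol 8.2 deals with a patient who, for whatever reason, requires another agent with demonstrated efficacy in psoriasis. For that patient, "discontinuation from the study occurs prior to introduction of the new agent". The bullet belongs to a list whose lead-in says that patients stop study drug, "complete the Post-Treatment Follow-up, and then permanently discontinue from the study in the following circumstances". Section 8.1.1 gives the same order for anyone permanently stopping investigational product: such patients "should complete the Post-Treatment Follow-Up and then be permanently discontinued from the study".

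**The permission.** Protocol 5.1.3 says that, for patients who have entered follow-up, "psoriasis therapy with another agent(s), as determined appropriate by the investigator, is allowed". Protocol 7.7 repeats the whole sentence: "For patients who have entered the Post-Treatment Follow-Up Period, psoriasis therapy with another agent(s), as determined appropriate by the investigator, is allowed". SAP 5.1 carries it as well.

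**The timing.** Footnote r of the Schedule of Activities says that when a patient stops study drug early, "the patient will complete the ETV and then enter the Post-Treatment Follow-up Period (Visit 801 and Visit 802"). The schedule puts Visit 802 at 12 weeks after the last visit.

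**The cross-reference.** The closing paragraph of 8.2 says that patients leaving prematurely "should complete AE and other safety follow-up per Section 2 (Schedule of Activities), Section 5.1.3 (Post-Treatment Follow-up Period"), along with Sections 9.2 and 9.4.

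**The concern.** The bullet in 8.2 makes leaving the study the condition for starting the new agent. The same section treats leaving the study as the last of three steps, after study drug has been stopped and follow-up completed. The permission in 5.1.3, 7.7 and SAP 5.1 applies one step earlier, while the patient is still in the study.

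Section 8.2 is where a site would look when a patient needs to change therapy. Two errors are possible:

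- A site that follows the bullet with its lead-in would hold back effective therapy through the whole follow-up period, from a patient who by the bullet's own terms requires it.
- A site could instead end participation at once so that the agent can start. Visits 801 and 802 would then be lost, with their adverse event, laboratory and C-SSRS assessments and the Visit 802 immunogenicity sample.

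The first error also defeats the reason given in Appendix 7 for adding the permission, which was faster access to other treatment for patients not benefiting from study drug.

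**Working it through.** There is no sample size, power or error rate to recompute. The check compares the texts and then works out the timing.

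**Step 1: order of events under each rule**

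| Source | Order |
|---|---|
| 8.2 lead-in | stop drug → complete follow-up → leave study |
| 8.1.1 | stop drug → complete follow-up → leave study |
| 8.2 last bullet | leave study → new agent |
| 8.2 bullet with its lead-in | stop drug → complete follow-up (Visit 802) → leave study → new agent |
| 5.1.3, 7.7, SAP 5.1 | stop drug → enter follow-up → new agent allowed |

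The fourth and fifth rows place the new agent on opposite sides of the follow-up period.

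**Step 2: length of the difference**

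Inputs from the Schedule of Activities: Visit 801 is the last visit + 4 weeks, Day 29 ± 5. Visit 802 is the last visit + 12 weeks, Day 85 ± 5.

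- Day convention: 29 − 1 = 28 days = 4 weeks, so the last visit counts as Day 1.
- Visit 802: 85 − 1 = 84 days; 84 / 7 = 12.0 weeks.
- Earliest in window: 80 − 1 = 79 days; 79 / 7 = 11.3 weeks.
- Latest in window: 90 − 1 = 89 days; 89 / 7 = 12.7 weeks.
- Under 5.1.3 and 7.7: the agent is allowed from entry into follow-up, which for early discontinuers comes directly after the early termination visit, so 0 days.
- Difference: 84 − 0 = 84 days, range 79 to 89.

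**Step 3: is it resolved elsewhere?**

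The closing paragraph of 8.2 points to 5.1.3, but for adverse event and other safety follow-up. It does not say which rule governs the new agent. Nothing else in either document ranks one rule above the other.

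**Step 4: likely origin**

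All the conflicting wording is current; Appendix 7 is used here only for origin and intent. It records for 5.1.3: "Added ability for patients to receive psoriasis therapy with another agent(s"). It shows the same sentence in its revised 7.7. The only 8.2 change that it lists or displays concerns systemic hypersensitivity events. The last bullet of 8.2 appears not to have been aligned when the permission was added.

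**Step 5: effect on the analysis**

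The maintenance endpoints concern response on mirikizumab, and both rules bar an added agent while study treatment continues. The planned efficacy estimates are therefore unchanged. PASI and sPGA are also scheduled at Visits 801 and 802, so follow-up scores could reflect another agent or not, depending on the rule a site applied.

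**The case against.** The strongest reply is that the protocol uses the word *study* loosely, often to mean the treatment period:

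- The schedule's abbreviations define LV as the last study visit, yet follow-up is timed from it.
- Section 7.4 keeps escalated patients on 250 mg until they complete the study or discontinue early, although follow-up has no dosing.
- Section 7.8.2.1 pairs discontinuation from the study with receiving no further doses.
- Section 5.1.3 has patients discontinue early and then enter follow-up.

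On that usage the bullet means only that the patient leaves the treatment period before the new agent starts, which agrees with 5.1.3. The provisions can also be read in sequence: the bullet addresses a patient still on drug, and the permission a patient already in follow-up. A site reading to the end of 8.2 is referred to 5.1.3, and 7.7, the natural place to check other therapy, repeats the permission.

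Part of this stands. The terminology is loose, the intent can be worked out, and a delay would require a site to overlook two explicit protocol permissions. Nothing in the documents shows that sites will do so. The change table in Appendix 7 is also not exhaustive, since it does not list the change to 7.7, so the account of the origin is an inference.

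The reply fails on the main point. The bullet's own lead-in separates stopping drug, completing follow-up and leaving the study, and 8.1.1 does the same. Within 8.2, leaving the study is the final step, and a looser sense borrowed from other sections does not override the sentence that introduces the bullet. The reference to 5.1.3 is limited to safety follow-up.

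**Conclusion.** The concern holds as a minor wording conflict in current text. Read with its lead-in, the last bullet of Protocol 8.2 delays another effective agent by 84 days (79 to 89 within the window) compared with Protocol 5.1.3, 7.7 and SAP 5.1.

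That figure assumes a site that applies the bullet literally and a patient who would otherwise start the agent on entering follow-up. The documents give no number of such patients and cannot show how sites will behave. Confidence is high that the wording conflicts; no claim is made about how often a delay would occur. What is at stake is patient management and the completeness of follow-up data.

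**What to change.** Reword the end of the last bullet of Protocol 8.2 so that *discontinuation from study treatment and entry into the Post-Treatment Follow-Up Period occur prior to introduction of the new agent*. This keeps the bar on adding another agent during study treatment, keeps the patient in follow-up through Visit 802, and agrees with 5.1.3, 7.7 and SAP 5.1.

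The cost is one phrase, made in the next protocol amendment or in a clarification letter to sites. Visits, data collection and analyses stay as they are, and the SAP needs no edit.
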